Date: December 20, 2016

Principal Investigator: [name]

Application Number: IRB00081746 (IND # 128487 – IND Sponsor: [name])

Study Title: Safety, Efficacy, and Feasibility of High-dose Cholecalciferol in Pediatric Patients with Cystic Fibrosis

Principal Investigator: [name]

Application Number: IRB00081746 (IND # 128487 – IND Sponsor: [name])

Document: Protocol to accompany reported study results

NCT02613884

Date: December 20, 2016

Principal Investigator: [name]

Application Number: IRB00081746 (IND # 128487 – IND Sponsor: [name])

JHM IRB - eForm A – Protocol

Safety, Efficacy, and Feasibility of High-dose Cholecalciferol in Pediatric Patients with Cystic Fibrosis

1. Abstract

Children and adults with Cystic Fibrosis (CF) are at risk of developing a vitamin D deficiency or insufficiency, defined as a 25-hydroxyvitamin D (25OHD) serum blood level <30 ng/mL. Greater than 85% of people with CF have pancreatic insufficiency, which contributes to poor absorption of fat soluble vitamins and dietary fats. A 25OHD level greater than 30 ng/mL has been shown to provide improvements to markers of inflammation in adults with CF and is known to improve bone mineral density and prevent bone fractures in all populations, including CF. This study will assess the safety of a one-time high dose of cholecalciferol or vitamin D3 along with efficacy and feasibility of providing this therapy.

Children between the ages of 3 years and 18 years (inclusive), with a 25OHD level <30 ng/mL will be provided with a vitamin D3 supplement of 250,000 international units (IU) observed in our CF clinic. We hypothesize that this one-time, oral, high dose of vitamin D3 will safely and effectively raise the 25OHD level to above 30 ng/mL.

Safety will be monitored using a tiered safety protocol. Within the first tier, a serum calcium level and a serum phosphorus level will be measured at 1 week and 3 months following the dosage. This timing is appropriate as cholecalciferol has a half-life of 2-3 weeks and these timed levels would be at or near the middle of the 25-OHD range. A second tier safety evaluation will only be done if serum calcium levels or serum phosphorus levels are elevated. For this second tier, the participant will have a parathyroid hormone level measured (PTH) as well as a spot urine calcium to creatinine ratio.

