Vitamin D toxicity or hypervitaminosis D is characterized by elevated serum calcium levels or hypercalcemia (14). Due to the hypercalcemia, acute symptoms of toxicity can include muscle weakness, confusion, vomiting, anorexia, polyuria and polydipsia. In addition, hypercalcemia can be chronic, and those symptoms of intoxication from hypervitaminosis D could include bone demineralization, pain, and nephrocalcinosis.

Therefore, we believe STOSS therapy will efficaciously, safely and feasibly increase vitamin D levels to above 30 ng/mL in our pediatric CF population. We hypothesize that STOSS therapy

Date: December 20, 2016

Principal Investigator: [name]

Application Number: IRB00081746 (IND # 128487 – IND Sponsor: [name])

administered once in clinic as witnessed by a designated clinician, will maintain 25OHD levels greater than or equal to 30 ng/mL without instances of hypercalcemia (7).

4. Study Procedures

The study is a phase 2 single arm study that will assess the safety, feasibility and efficacy of a high dose of vitamin D3 as cholecalciferol in Cystic Fibrosis pediatric patients with a 25OHD level <30 ng/mL. The members of the study team will enroll 30 participants who have consented and meet eligibility criteria, including a baseline 25OHD level <30 ng/mL which is measured annually, at a minimum, as a part of the current standard of care. All patients with CF, will be consented to participate upon having his/her annual lab work collected.

As patients present with a 25OHD level < 30 ng/mL they will be screened to see if they meet full eligibility criteria for enrollment. This will include a phosphorus level and spot urine calcium to creatinine ratio which will be collected at their CF visit (patients seen at the St. Petersburg office) or within 2 weeks prior to their visit if in Sarasota or Tampa. (See section 5 for complete inclusion/exclusion criteria). Screening will also consist of a urine pregnancy test to be completed the day of the administration of the high dose of vitamin D.

After a patient meets full eligibility criteria, they will be enrolled in the study and we will administer the 250,000 IU vitamin D3 at that visit. Upon administration, each participant will be provided with an oral, one-time dosage of vitamin D3 (cholecalciferol) in the form of capsules that will be swallowed; the capsule cannot be crushed or dissolved in anything in order to be administered.

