There will not be a placebo group, as the study design does not support this; providing a placebo is not ethical in this population for this condition.

If a patient does not complete the study for any reason, meaning they do not get each set of lab work completed, their results up to that point in time will still be used in the study but their duration of participation will be noted in the results section. Every effort will be made to contact patients who are lost to follow up to ascertain the reason for withdrawal.

Date: December 20, 2016

Principal Investigator: [name]

Application Number: IRB00081746 (IND # 128487 – IND Sponsor: [name])

| Study Procedures | Study Time-points | | | | | | | |
|---|---------------------------|---------------|---------------------|---|------------------------------|--|---------------------------|------------------------|
| | Screening/ Eligibility | Base- line | Week 1 +/- 3 day | Week 1 B.*** Week 1+/- 14 days | Week 12 +/- 30 days | Week 12 B.*** Week 12 +/- 42 days | Week 26 +/- 30 days | Week 52 +/- 30 days |
| Informed Consent | X | | | | | | | |
| 25OHD Lab | X | | | | X | | X | X |
| Screening / Eligibility Verification (including pregnancy test) | X | | | | | | | |
| Eligibility screening: Spot Urine Calcium to Creatinine Ratio | X | | | | | | | |
| Study Registration | | X | | | | | | |
| Medication Review* | | X | | | X | | X | X |
| STOSS Vitamin D3 Administration | | X | | | | | | |
| Serum Calcium Test & Hypercalcemia Monitoring | | | X | X | X | X | | |
| Serum Phosphorus | X | | X | X | X | X | | |
| Parathyroid Hormone (PTH) Level (2 nd tier only) | | | | X | | X | | |
| Spot Urine Calcium to Creatinine Ratio (2 nd tier only) | | | | X | | X | | |
| Administration of Appendix A Questionnaire | | | X | | | | | |
| Adverse Event Assessment** | | X | X | X | X | X | X | X |

* Medication review will consist of surveying the patient's current daily maintenance dosage for vitamin D as previously prescribed.

** AEs and SAEs are defined per 21CFR312.32. All adverse events will be monitored and processed from study start until 30 days after study product administration. All adverse events deemed related to known vitamin D supplementation risks and/or study procedures will be monitored for 12 months post drug administration.

Date: December 20, 2016

Principal Investigator: [name]

Application Number: IRB00081746 (IND # 128487 – IND Sponsor: [name])

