*** 2nd tier safety assessment using PTH will only be performed in the event serum calcium levels or serum phosphorus levels are elevated greater than the upper limit of normal for age. A spot urine calcium to creatinine ratio will be done. Repeat calcium and phosphorus will be provided every 2 weeks until normalized.

5. Inclusion/Exclusion Criteria:

1. Exclusion Criteria:

- a. Any history of kidney disease, kidney stones, or on dialysis
 - b. Any history of hypercalcemia above upper limits of normal for age within the last six months (see appendix B for normal calcium levels).
 - c. Elevated serum phosphorus level at screening
 - d. Elevated spot urine calcium to creatinine ratio at screening
 - e. Abnormal serum creatinine level 2 times the upper limit of normal for age within the last 6 months
 - f. History of unresolved, abnormal liver function (ALT or AST > 4 times upper limit of normal (ULN)) or any history of portal hypertension.
 - g. Pregnant or breast feeding adolescent females; upon enrollment, will test urine sample for pregnancy in females 8 years and older
 - h. Any history of parathyroid disorders
 - i. Inability to swallow pills by mouth
- ### 2. Inclusion Criteria:
- a. Children with Cystic Fibrosis \geq 36 months of age
 - b. Serum/blood 25OHD level < 30 ng/mL
 - c. Ability to provide valid informed consent to be a part of the study
 - d. Negative urine pregnancy test upon enrollment

6. Drugs/ Substances/ Devices

This trial is being conducted under Investigational New Drug (IND) application # 128487 – IND Sponsor: [name]; all relevant FDA regulations will be followed.

Cholecalciferol (Vitamin D3) capsules from Biotechpharmaceutical will be used. Each capsule has 50,000 International Units of Vitamin D3. Each participant will be provided with 250,000 IU Vitamin D3 (5 capsules) regardless of age, sex or 25OHD level.

The dosage of 250,000 IU Vitamin D3 has been shown to be safe and effective in raising the 25OHD level in adult patients with CF and dosages higher than this have been shown to be safe and effective at raising 25OHD levels in pediatric patients as young as 36 months old with dosages of 100,000 IU Vitamin D3 in addition to pediatric patients 12 years old receiving 400,000 IU Vitamin D3 as a one-time dosage without any adverse events, including hypercalcemia.

The safety of high dose of Vitamin D3 has not been evaluated in pediatric CF patients in the U.S.

7. Off-Treatment and Off-Study Criteria

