The aim of the study is to determine safety and feasibility of a single high dose (250,000 IU) oral vitamin D3 for the treatment of vitamin D insufficiency/deficiency in pediatric cystic fibrosis patients. The study is therefore not powered to detect a difference in a clinically important endpoint. We intend to consecutively enroll 30 patients in the study. A sample size of 30 should be sufficient to determine the safety and feasibility and to also estimate the parameters needed to perform a definitive sample size and power estimation of a large-scale RCT if safety and feasibility are shown in the current study. An appropriate sample size and power calculation based on the parameters obtained in this study will be presented in a future large-scale RCT protocol.

Date: December 20, 2016

Principal Investigator: [name]

Application Number: IRB00081746 (IND # 128487 – IND Sponsor: [name])

Early Stopping Rules:

1. Participants who experience hypercalcemia as defined by a serum calcium greater than 13.5 mg/dL or with a spot urine calcium to creatinine ratio >2 times ULN will be allowed to stop the study and resume standard of care of treatment of their vitamin D insufficiency and will be required to receive treatment for their severe hypercalcemia (defined below in section 10 under “steps taken to minimize the risks”).
2. Participants who experience a 25OHD level as defined by a level of >100 ng/mL will continue to be followed in the study and be monitored for hypercalcemia or hypercalciuria with the study protocol.

10. Risks:

Risks of the trial include:

- a. Venipuncture risks at baseline, 1 week, 3 mo, 6 mo, & 12 mo;
- b. Swallowing risks at baseline;
- c. risk of hypervitaminosis D at 3 mo, 6 mo, & 12 mo;
- d. risk of hypercalcemia at 1 week, 3 mo, 6 mo, & 12 mo;
- e. risk of renal stones at 1 week, 3 mo, 6 mo, & 12 mo;
- f. risk of continued vitamin D deficiency/insufficiency regardless of treatment throughout the study duration;
- g. Other minor risks associated with the trial include upset stomach (nausea) and taking a vitamin supplement by mouth.

Steps taken to minimize the risks:

- a. Standard precautions will be used with other venipuncture occurrences;
- b. Patients will be monitored as they are administered their one-time, oral, high dose vitamin D in CF Clinic. They will be provided with water to take it with by mouth;

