Patient data will be stored for research purposes as a HIPAA defined limited data set in a secure, password protected web-based electronic data capture (EDC) system. Each patient will be assigned a unique Participant ID number in the EDC system. Access to the EDC system will be restricted to those users identified as part of the research study team and permission will be granted based on levels of access deemed necessary for their role. Data extractions as well as modifications or edits to data will be logged appropriately to adhere to audit trail requirements. No financial risks to participants have been identified.

11. Benefits

Previous studies of a high dose of vitamin D3, in adults with CF, have shown that they have a decrease in markers of inflammation, specifically interleukin and TNF. Studies have also shown that adequate vitamin D may help to maintain or improve lung function although this has not been proven. Adequate vitamin D is widely known to improve bone mineral density in children and adults, with and without CF. It is hoped that this study might provide additional information regarding the role of a high dose of vitamin D in relation to sustaining an appropriate serum 25OHD level for up to 12 months, safely and feasibly.

12. Costs

Labs:

Serum calcium levels measured at 1 week post administration of the high dose vitamin D3 and at the 3 month visit post administration of vitamin D3 will be covered by a grant. The cost of each serum calcium measurement will be billed as "research" and will cost approximately \$62.64 for each draw.

Date: December 20, 2016

Principal Investigator: [name]

Application Number: IRB00081746 (IND # 128487 – IND Sponsor: [name])

Serum phosphorus will be measured at baseline, 1 week post administration of the high dose vitamin D3 and again at the 3 month visit along with serum calcium and 25OHD. The cost of serum phosphorus will be billed as “research” and is \$31.42 per draw and will be covered by a grant provided by the ACH foundation.

Spot urine calcium to creatinine ratio levels will be done as a part of the screening process for this study as well as if a participant has a serum calcium level >ULN. The cost of one spot urine calcium to creatinine ratio is \$73.52. This will cost approximately \$2205.60 for the screening purpose of this test for 30 participants.

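### Early Stopping Rules 1 and 2 rely on post-dose urinary calcium that the schedule does not measure in children with normal serum values, nor in any child first found above 100 ng/mL 25OHD at week 26 or 52

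*Combined protocol and SAP*

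**What the plan says.** **Before the dose.** Section 4 describes eligibility screening: "This will include a phosphorus level and spot urine calcium to creatinine ratio which will be collected at their CF visit" (or up to two weeks earlier at the two other sites). Section 5 excludes on "Elevated spot urine calcium to creatinine ratio at screening". Every enrolled child therefore starts with a normal ratio.

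**After the dose.** The Abstract limits further testing: "A second tier safety evaluation will only be done if serum calcium levels or serum phosphorus levels are elevated". The calendar row reads "Spot Urine Calcium to Creatinine Ratio (2 nd tier only" and has entries only in the Week 1 B and Week 12 B columns. Section 4 states that calcium, phosphorus and PTH are not measured as safety tests after week 12.

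**The rules.** In Section 9, Early Stopping Rule 1 covers children with calcium above 13.5 mg/dL "or with a spot urine calcium to creatinine ratio >2 times ULN". Rule 2 keeps children with 25OHD above 100 ng/mL in follow-up, to "be monitored for hypercalcemia or hypercalciuria with the study protocol". Section 10 lists "risk of renal stones at 1 week, 3 mo, 6 mo, & 12 mo".

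**The analysis.** Section 9 plans the mean and SD of week-1 serum calcium, the proportion with raised calcium with a 95% confidence interval, and adverse event counts. It plans no summary of urinary calcium.

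**The concern.** The protocol treats a raised urine ratio as a signal in its own right. It is an exclusion criterion, it has its own consult and repeat schedule in Section 4, and it is one of two alternative criteria in Rule 1. Yet whether a child is tested after the dose depends on a different abnormality having appeared first.

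Safety is the primary objective. If the report says that the stopping criteria were monitored and none was met, a reader will take this to include urinary calcium in all participants. For children with normal serum values there would be no data behind that statement. Rule 2 has the further problem that it describes monitoring which, at two of the three post-dose 25OHD visits, the schedule does not contain.

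**Working it through.** **Step 1. The schedule, by time point** (Abstract, Section 4, calendar and footnote; ULN = upper limit of normal for age).

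| Time point | Serum safety tests | 25OHD | Urine ratio |
|---|---|---|---|
| Screening | phosphorus | yes | every child |
| Week 1 | calcium, phosphorus | no | if calcium or phosphorus > ULN |
| Week 12 | calcium, phosphorus | yes | Section 4 text: if calcium > ULN; Abstract and calendar footnote: second tier after calcium or phosphorus |
| Weeks 26 and 52 | none | yes | none |

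Section 12 also names only raised calcium as the post-dose reason for a urine test, so the trigger is not stated consistently. A child already flagged has repeats until values normalise. The table concerns children not yet flagged.

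**Step 2. The rules applied to each kind of child.**

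- *Calcium above ULN but not above 13.5 mg/dL.* A urine ratio is obtained, and Rule 1 can be met through urine alone. The alternative works here.
- *Phosphorus raised, calcium normal.* A urine ratio is obtained at week 1. At week 12 it depends on which passage is followed.
- *Both normal.* No urine ratio is scheduled. The urine criterion is not assessed.
- *25OHD first above 100 ng/mL at week 12.* Calcium and phosphorus are drawn at that visit. Urine follows only if a serum value is raised, and nothing further is scheduled if none is.
- *25OHD first above 100 ng/mL at week 26 or 52.* No calcium, phosphorus or urine test is scheduled at or after that visit. Rule 2 has nothing to operate on.

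**Step 3. The plan's own figures.** Section 12 prices one urine ratio at $73.52.

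- Screening: 30 × 73.52 = $2,205.60, as stated "for the screening purpose of this test for 30 participants".
- Post-dose: 3 children × 2 time points × 73.52 = 6 × 73.52 = $441.12, as stated.

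Both reproduce. The budget is 30 tests before the dose and 6 after it, in 3 of 30 children (10%). The three is the number at which Section 12 says the study is held for hypercalcemia. It is not a forecast, and phosphorus triggers could add to it.

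**Step 4. What one universal post-dose sample would give.**

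- With no case in 30, the exact two-sided 95% upper limit is 1 − 0.025^(1/30) = 11.6%.
- The documents give no rate of hypercalciuria with normal serum values, so a range is assumed. The chance of at least one case in 30 tested is 1 − (1 − p)^30: 26.0% at p = 1%, 45.5% at 2%, 78.5% at 5%, 95.8% at 10%.
- Under the present schedule the chance that such a child has a scheduled urine test is zero at every p.

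**The case against.** The tiering is deliberate and openly described, and Section 4 says two endocrinologists reviewed and approved the safety measures. The primary safety endpoint is week-1 serum calcium; hypercalciuria is not an endpoint. Rule 2 refers to monitoring under the protocol, which can be read as the tiers and nothing more. Rule 1 is phrased as a case of hypercalcemia and permits an individual child to leave the study; it is not a trial-level boundary. All of this stands as a defence of tiering. It does not reconcile the rules with a schedule that cannot supply what they refer to, and at weeks 26 and 52 there is no first tier to start from.

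Three stronger readings are tempting, and the documents do not support them.

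- *The urine criterion can never be met, or hypercalciuria cannot be seen.* The criterion can be met by any child flagged on serum values. Section 10 also lets the principal investigator decide on further testing after hypervitaminosis D, hypercalcemia or hyperphosphatemia, and related adverse events are followed for 12 months, so a symptomatic stone could be reported. These routes are discretionary or symptom-driven. What is missing is a scheduled measurement.
- *The reported hypercalciuria rate will be biased towards zero.* Section 9 plans no such rate, so there is no estimate to be biased.
- *A confidence limit from the few children tested shows how little will be known.* Those children are selected for a raised serum value. A limit computed from them does not describe the cohort and should not be set against one from all 30.

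**Conclusion.** Wrong as written, in a limited sense: Rules 1 and 2 do not agree with the calendar and the procedure text. The conflict is plainest for Rule 2 at weeks 26 and 52, where the monitoring it describes has no scheduled calcium or urine test. For Rule 1 it is confined to children whose serum calcium and phosphorus stay normal. The week-12 urine trigger is a separate contradiction between passages.

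The effect is on what the trial may conclude. A laboratory safety statement can rest on serum calcium and phosphorus at weeks 1 and 12; it cannot include absence of hypercalciuria. How many children this concerns depends on how many have raised serum values, which the documents do not predict. How much it matters clinically depends on a rate they do not give. The conclusion itself rests only on the text and needs neither figure. The absence of a universal post-dose urine sample is not an error in itself; adding one is at most a cheap improvement.

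**What to change.** 1. **Reconcile the passages.** The sponsor and its endocrinologists should bring Rules 1 and 2 into agreement with the Abstract, the Section 4 text, the calendar and footnote, the further-testing provision in Section 10, and Section 12. This includes the week-12 urine trigger, and whether the urine criterion in Rule 1 is meant to apply only to children already in the second tier. No threshold or clinical action is proposed here. Cost: wording only, unless the sponsor decides to add tests.

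2. **Limit the conclusion in Section 9.** State that post-dose urinary calcium is not systematically assessed in children with normal serum values, so the laboratory safety conclusion covers serum calcium and phosphorus only and makes no claim that hypercalciuria was absent. Cost: wording only.

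3. **Optional, if funded.** Collect a spot urine from all participants at the existing week-1 laboratory visit. Report the paired change from screening and the proportion above the Appendix C limit with an exact 95% confidence interval. Because raised ratios are excluded at screening, the result would be directly interpretable, and no extra venipuncture is needed. Cost: 30 × $73.52 = $2,205.60. This is a floor, because a raised ratio would bring in the consult and repeat tests of Section 4. It would leave later time points uncovered and would not serve Rule 2, since 25OHD is first measured after the dose at week 12.

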Patient data will be stored for research purposes as a HIPAA defined limited data set in a secure, password protected web-based electronic data capture (EDC) system. Each patient will be assigned a unique Participant ID number in the EDC system. Access to the EDC system will be restricted to those users identified as part of the research study team and permission will be granted based on levels of access deemed necessary for their role. Data extractions as well as modifications or edits to data will be logged appropriately to adhere to audit trail requirements. No financial risks to participants have been identified.

11. Benefits

Previous studies of a high dose of vitamin D3, in adults with CF, have shown that they have a decrease in markers of inflammation, specifically interleukin and TNF. Studies have also shown that adequate vitamin D may help to maintain or improve lung function although this has not been proven. Adequate vitamin D is widely known to improve bone mineral density in children and adults, with and without CF. It is hoped that this study might provide additional information regarding the role of a high dose of vitamin D in relation to sustaining an appropriate serum 25OHD level for up to 12 months, safely and feasibly.

12. Costs

Labs:

Serum calcium levels measured at 1 week post administration of the high dose vitamin D3 and at the 3 month visit post administration of vitamin D3 will be covered by a grant. The cost of each serum calcium measurement will be billed as "research" and will cost approximately \$62.64 for each draw.

Date: December 20, 2016

Principal Investigator: [name]

Application Number: IRB00081746 (IND # 128487 – IND Sponsor: [name])

Serum phosphorus will be measured at baseline, 1 week post administration of the high dose vitamin D3 and again at the 3 month visit along with serum calcium and 25OHD. The cost of serum phosphorus will be billed as “research” and is \$31.42 per draw and will be covered by a grant provided by the ACH foundation.

Spot urine calcium to creatinine ratio levels will be done as a part of the screening process for this study as well as if a participant has a serum calcium level >ULN. The cost of one spot urine calcium to creatinine ratio is \$73.52. This will cost approximately \$2205.60 for the screening purpose of this test for 30 participants.

We will additionally budget the cost of three participants requiring this test as a measure of safety, as this will be 10% of our overall goal number of study participants. Once we have 10% of our study participants with hypercalcemia and requiring additional safety testing, the study will be held until the DSMB can review.. The cost of three participants requiring this test at week 1 and at month 3, will cost \$441.12 (\$73.52 per test).

The cost for the urine pregnancy tests will be about \$1.98 per test or \$49.63 per box of 25 tests. We do not expect to need more than 25 pregnancy tests since these will only be used for female participants greater than 8 years old.

25OHD level is a part of the standard of care for pediatric patients with Cystic Fibrosis and will be measured for “baseline” measures prior to enrollment in the study and upon annual exam. Therefore, the cost fits within the usual cost to the participant even if they weren’t participating in the study. In addition, each time they are required to have it re-measured at 3 mo, 6 mo & 12 mo it will continue to be a part of the standard of care for assessing their vitamin D. There will be standard costs associated with it that the participant would be paying even if they weren’t participating in this study.

Vitamins/Supplements:

Vitamin D3 water miscible form will be purchased via grant funds from BioTechPharmaceutical.com for \$18.00 per 100 capsules of a water soluble and vegetarian vitamin D3 – 50,000 IU per capsule (18 cents per capsule or maximum cost per STOSS dosage of 250,000 IU is \$0.90).

CF specific vitamins are currently prescribed to all patients upon diagnosis. Therefore, participants will already be prescribed these as a part of the standard of care for the nutritional management of pediatric patients with CF and pancreatic insufficiency. Patients who are pancreatic sufficient will be on a standard regular multivitamin with minerals as a part of the standard of care. Neither of these will accrue additional cost to our center or to the patient.

Other: Support Personnel

A research coordinator will act as a part of the research time. He/she will assist in approaching eligible patients to obtain consent for participation in this study, scheduling necessary lab work, conducting the 10-item questionnaire and inputting the necessary data into the Red Cap database

Date: December 20, 2016

Principal Investigator: [name]

